7.3 The randomisation scheme: N/a

7.3.1 Method of implementing the allocation sequence: N/a

7.4 Blinding

Laboratory staff performing the faecal VOCs analysis will be blinded to the patient's diagnosis and response to treatment in those with IBD.

Faecal VOCs results will not be available to clinical staff who are making diagnoses and assessing response to treatment in IBD.

7.5 Unblinding: N/a

7.6 Baseline data

Demographic, environmental and clinical information will be collected onto standard forms:

- Demographic information will include age, gender, ethnicity
- Clinical information will include anthropometry, main presenting gastrointestinal symptoms and signs, current diet (e.g. vegan), current medication, treatment with oral/parenteral antibiotics or anti-fungal agents in the last 3 months
- Environmental factors will include: number of siblings at home, smoker in the household, household pets, urban/rural residence, foreign travel in last 3 months

The results of routine clinical baseline investigations if done will be recorded:

- In blood: haemoglobin, white cell count, inflammatory markers (platelets, C-reactive protein, ESR), albumin, liver function tests, urea, creatinine, test for coeliac disease
- In stool: calprotectin, C. difficile toxin, bacterial culture
- Imaging: X rays and scans

Further investigations will be planned according to the initial clinical assessment in accordance with usual clinical practice.

7.7 Trial assessments

A diagnosis of IBD will be based on gastrointestinal endoscopy and biopsy and imaging and IBD type classified according to standard clinical guidelines (Crohn's disease, ulcerative colitis, indeterminate colitis; Levine 2014). The distribution of disease and associated manifestations (e.g. presence of fistulas) in CD will be classified according the Paris classification (Levine 2011). The severity of IBD at initial diagnosis will be graded according to paediatric-specific disease activity scores: weighted Paediatric Crohn's Disease Activity Index (wPCDAI) and Paediatric Ulcerative Colitis Activity Index (PUCAI; Ruemmele 2014). Treatment of IBD will be provided by clinical staff and follow established clinical guidelines.

For other conditions, specific investigations and diagnosis will be guided by clinical assessment; e.g.

Faecal volatiles in children with inflammatory bowel disease

serum anti-tissue transglutaminase antibodies and/or small bowel biopsy for the diagnosis of coeliac disease; stool bacterial culture for infectious diarrhoea. Appropriate treatment will be provided by clinical staff.

The clinical records of all children will be reviewed at 3 months after recruitment and information regarding results of investigations and diagnosis/diagnoses will be recorded.

In children with IBD, a further stool sample will be requested at 3 months. This will be used for measurement of faecal calprotectin as part of routine clinical care and, if young people or parents/guardians agree, for repeat measurement of VOCs as described above. Treatment received will be recorded and current disease activity determined. Clinical remission in CD will be defined as a wPCDAI ≤12.5 and in UC as PUCAI <10 points in the absence of corticosteroid treatment (Ruemmele 2014).

- 7.8 Long term follow-up assessments: Participants will not be followed-up after 3 months.
- 7.9 Qualitative assessments Nested studies: N/a
- 7.10 Withdrawal criteria: N/a

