7.1.2 Screening

The clinical team will review referral information, including the results of any investigations performed to date (e.g. faecal calprotectin done by the referring clinician). They will identify children in whom they consider that IBD is either the working diagnosis or amongst the differential diagnoses.

Consistent with routine clinical practice, children referred to out-patient clinics will be sent a letter including guidance and the consumables required to collect a faecal sample to bring to clinic. Young people or parents/guardians will be asked to collect a stool sample the day before or morning of the clinic visit. They will be instructed to collect 2/3 good scoops of stool using a spatula, or an equivalent volume of liquid stool, into a hard plastic Sterilin tube and wearing a pair of disposable gloves. The tube will be double-bagged using zip lock plastic bags. If collected the day before, they will be asked to store the sealed bag in the home freezer (to stop fermentation) and then bring it to the clinic at ambient temperature. They will be provided with a plastic bag for safe disposal of the consumables used. Children attending the ward for review or directly for investigational procedures will also be requested to provide a stool sample. Stool samples will be used for the measurement of faecal calprotectin for the assessment of intestinal inflammation as part of routine clinical practice.

No additional hospital visits are required to participate in the study. Therefore, no payments (e.g. travel expenses) will be made to participants.

Children who do not meet eligibility criteria at the time of screening will be eligible for rescreening should they present for clinical assessment on a subsequent occasion.

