10.1 Sample size calculation

Given the high sensitivity of FC in identifying children with IBD (0.98; 95% CI 0.95–1.0; Henderson 2014), we have based the sample size calculation on demonstrating that faecal VOCs have a higher specificity in identifying IBD than FC. We require 88 children with suspected IBD to demonstrate that VOCs has a better specificity of 0.80 than the specificity of 0.68 reported for FC (Henderson 2014) with 80% power at the 0.05 significance level.

Given the non-invasive nature of our study, we plan to increase the number of children recruited to also assess the ability of VOCs to differentiate between CD and UC. We plan to exceed the numbers of adults with active IBD that demonstrated excellent separation between CD and UC in our previous study (110 patients; Ahmed 2016). Our hospital IBD databases indicate that amongst new cases, two-thirds have CD and one-third UC. In our clinical experience, IBD is confirmed in 1 in 2 children with suspected IBD. To achieve sufficient power, we will recruit a total of 286 children with suspected IBD.

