10.5 Adjusted analysis - N/a

10.6 Interim analysis and criteria for the premature termination of the trial: N/a

10.7 Subject population

All participants in whom analysis of faecal VOCs is completed will be included in the study analysis.

The analysis of faecal VOCs according to response to treatment in IBD will include all children diagnosed with IBD in whom faecal VOCs are analysed 3 months after treatment.

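### Non-IBD labels may rest on FC-informed clinical assessment without required endoscopy, and all labels are pooled, so missed FC-negative IBD would lower apparent VOC specificity

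*Protocol*

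**What the plan says.** Protocol 7.7 sets the two labels differently. For IBD: "A diagnosis of IBD will be based on gastrointestinal endoscopy and biopsy and imaging". For everything else, "specific investigations and diagnosis will be guided by clinical assessment", with coeliac serology or biopsy and stool culture given as examples. Section 7.6 adds: "Further investigations will be planned according to the initial clinical assessment in accordance with usual clinical practice". Appendix 4 lists endoscopy only as an example of what usual care may call for. Diagnoses are taken from one record review at 3 months, and 7.8 rules out later follow-up.

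Section 1 (Background) reads differently. It describes upper and lower endoscopy and small bowel imaging as required at presentation in every child with suspected disease.

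FC is open to the clinicians. At screening they review referral information, "including the results of any investigations performed to date (e.g. faecal calprotectin done by the referring clinician"), and 7.1.2 has FC measured as routine practice. Blinding covers VOCs only: "Faecal VOCs results will not be available to clinical staff who are making diagnoses" (7.4).

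Section 10.1 bases the sample size on "demonstrating that faecal VOCs have a higher specificity in identifying IBD than FC". Section 10.3.2 compares confirmed IBD with alternative diagnoses, and 10.7 states: "All participants in whom analysis of faecal VOCs is completed will be included in the study analysis". Section 10.9 explores combinations of VOCs with FC against the same diagnoses.

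**The concern.** The comparator test can influence who is fully investigated, and the index test cannot. A child with IBD and a low FC may be less likely to be scoped and so more likely to be labelled non-IBD at 3 months. In the pooled analysis that child is a false positive for VOCs if VOCs detect the disease. When FC is scored on the same labels, the child is a true negative for FC.

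Specificity against FC is the quantity the study is sized on, and the planned difference is only 0.12, so a handful of mislabelled children matters. The protocol's description of the analysis does not separate non-IBD labels verified by endoscopy from those that are not, so a reader of the result could not tell whether this had happened.

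**Working it through.** **Inputs from the protocol.** Target VOC specificity 0.80; published FC specificity 0.68; power 80%; significance level 0.05; FC sensitivity 0.98 (95% CI 0.95 to 1.0) (10.1). 286 children, IBD confirmed in 1 of 2, so 143 IBD and 143 non-IBD (10.1, 10.2). VOC sensitivity 94% and 96% in adults (section 1).

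**Assumptions.** VOC sensitivity 0.95 in the missed children; m missed IBD cases among 143 labelled non-IBD; all m FC-negative.

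**Step 1: the plan's own figure.** A one-sample comparison with a fixed 0.68, two-sided 0.05, variance taken at 0.80, gives n = (1.960 + 0.842)² × 0.80 × 0.20 / 0.12² = 87.2, rounded up to 88. The stated 88 is reproduced, counting all 88 towards specificity. The design that reproduces it uses the published FC value as a constant.

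**Step 2: plausible m.** FC-negative children among 143 with IBD: 143 × 0.02 = 2.9, about 3; at the lower confidence limit 143 × 0.05 = 7.2, about 7; at the upper limit 0. These are the numbers if every such child is missed, so the range is 0 to 7.

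**Step 3: apparent specificity.**
- VOC = [0.80 × (143 − m) + 0.05 × m] / 143
- FC on study labels = [0.68 × (143 − m) + m] / 143
- m = 3: VOC = (112.0 + 0.15)/143 = 0.784; FC = (95.2 + 3)/143 = 0.687
- m = 7: VOC = (108.8 + 0.35)/143 = 0.763; FC = (92.48 + 7)/143 = 0.696

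**Step 4: power against 0.68 at n = 143**, same method as step 1: Φ[(p − 0.68)/√(p(1 − p)/143) − 1.96].

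| m | VOC specificity | Gap to fixed 0.68 | Power, n = 143 | FC on study labels | Gap on same labels |
|---|---|---|---|---|---|
| 0 | 0.800 | 0.120 | 0.95 | 0.680 | 0.120 |
| 3 | 0.784 | 0.104 | 0.86 | 0.687 | 0.098 |
| 7 | 0.763 | 0.083 | 0.65 | 0.696 | 0.068 |

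**Step 5: sensitivity to the assumptions.**
- With VOC sensitivity 0.80 in the missed children, VOC specificity is 0.787 (m = 3) or 0.771 (m = 7). With 0.50 it is (112.0 + 1.5)/143 = 0.794 or (108.8 + 3.5)/143 = 0.785.
- If the missed cases are FC-positive, they count against both tests. FC becomes 95.2/143 = 0.666 (m = 3) or 92.48/143 = 0.647 (m = 7), and the gap on the same labels is 0.119 or 0.117, almost unchanged from 0.12. The asymmetry therefore needs the missed cases to be mainly FC-negative.

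**The case against.** **A separate SAP is announced (section 10), and a sensitivity analysis belongs there.** This stands in part: the method can go in the SAP. But the protocol itself fixes how labels are made (7.7) and who is pooled (10.7), and a SAP can only use verification status if it has been captured.

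**Section 1 says endoscopy is needed in all suspected children, and 6.1 admits only children with suspected IBD and further evaluation planned.** If every child is scoped, the problem disappears. Sections 7.6, 7.7 and Appendix 4 do not make endoscopy a study requirement, so the share scoped is unknown. The documents do not show that any child will be missed, only that the design allows it.

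**The 3-month review already records results of investigations.** This stands. Endoscopy status is probably recoverable, so the request is mainly to code it. Whether FC was known before the work-up is not listed.

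**The bias runs against the study's hypothesis, so it is conservative.** This is true for a positive finding, but it does not help if the study fails to show the difference.

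**Stronger readings to resist.**
- A reader might infer that mislabelling also helps FC in the powered comparison. The calculation that reproduces 88 uses a fixed 0.68, so there only VOC specificity moves. FC gains only where it is assessed on study labels, as in 10.9 or a paired comparison.
- A reader might push to 10% mislabelled, or 14 children. If all are FC-negative, that implies FC sensitivity of 1 − 14/143 = 0.90, below the cited interval.
- A reader might want to say how far FC specificity would fall in scoped children only. FC-positive children are likely to be over-represented among them, so the direction is clear, but the size depends on endoscopy rates the protocol does not give.

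**Conclusion.** The concern holds as a possible bias of modest size. Non-IBD labels may rest on assessment informed by FC, without endoscopy as a study requirement, and the planned analysis pools them with verified labels. Within the cited FC sensitivity interval, 0 to 7 missed cases move VOC specificity from 0.80 to between 0.80 and 0.763. Even at three missed cases, power at n = 143 (0.86) stays above the planned 80%; at seven (0.65) it does not.

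These figures assume VOC sensitivity of 0.95, taken from adult data, and that every FC-negative child with IBD is missed. The effect shrinks if VOCs detect fewer of these children. A reader might conclude that the specificity result cannot be interpreted at all. The documents do not support that: the main estimate stays useful if its dependence on verification is shown.

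**What to change.** 1. Reconcile section 1 with 7.6, 7.7 and Appendix 4, so that it is clear whether endoscopy is expected in every recruited child or only where usual care leads to it.
2. At the planned 3-month record review, code for each child labelled non-IBD whether endoscopy was done and whether the FC result was known beforehand.
3. Keep the all-children analysis as the main one. Add VOC specificity, FC specificity and their paired difference (a) in endoscopy-verified children and (b) with a verification-bias correction, either Begg-Greenes or inverse-probability weights for endoscopy given FC and presenting features. Children with confirmed IBD count as verified.
4. State in the report whether the conclusion changes between these analyses.

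The cost is one or two coded items at a review already planned and one extra table, with no added procedure and no change to care. The correction has limits. It assumes that endoscopy depends only on recorded features, and it may be imprecise if few FC-negative children are scoped. The verified-only result has its own selection, so neither should replace the main analysis.

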Name: (please print): [name] Position: Professor of Biostatistics Date: 10/MAY/2017

KEY TRIAL CONTACTS

Chief Investigator	[name], Department of Clinical Sciences, Liverpool School of Tropical Medicine; Honorary Consultant Paediatrician, Alder Hey NHS Foundation Trust. [contact]; [contact]
Study Co-ordinator	Alder Hey Research Nurse: to be appointed
Sponsor	Alder Hey Children's NHS Foundation Trust, [name]. [contact]; e mail: [contact]
Joint-sponsor(s)/co-sponsor(s)	Liverpool School of Tropical Medicine, [name]; [contact]; e mail: [contact]
Funder(s)	NIHR Research for Patient Benefit
Clinical Trials Unit	Tropical Clinical Trials Unit, Liverpool School of Tropical Medicine, [name]; e mail: [contact]
Key Protocol Contributors	Full contact details including phone, email and fax numbers (If applicable)
Statistician	[name], Professor of Biostatistics, Liverpool School of Tropical Medicine, [name]; e mail: [contact]
Trials pharmacist	N/a
Committees	TMG: [contact]; [contact]

TRIAL SUMMARY

Trial Title	Evaluation of faecal volatile organic compounds in the diagnosis of paediatric inflammatory bowel disease		
Internal ref. no. (or short title)	Faecal volatiles in children with inflammatory bowel disease		
Clinical Phase	N/a		
Trial Design	Observation study of diagnostic test		
Trial Participants	Children (age <18 years) attending clinics in 3 paediatric gastroenterology referral centres in the UK in whom clinical assessment indicates that IBD is a possibility		
Planned Sample Size	286 children		
Treatment duration	N/a		
Follow up duration	3 months for each child recruited		
Planned Trial Period	April 1st 2017 to September 30 th 2019		
	Objectives	Outcome Measures	
Primary	To evaluate whether faecal VOCs at initial presentation to specialist paediatric gastroenterology services can distinguish children with IBD from those with other common gastrointestinal disorders	Faecal VOCs in IBD versus non-IBD gastrointestinal conditions at initial presentation to specialist paediatric gastroenterology review	

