STUDY FLOW CHART

VOCs in pIBD Flow chart

Study timeline

A. Study preparation: April - September 2017 (6 months)

- Study preparation will start on April 1st
- Ethical approval secured by end of July 2017
- SOPs and CRFs completed by end of August 2017
- Study database completed by end of September 2017
- Site-set-up and training completed by end of September 2017

B. Recruitment and follow-up: October 2017 - end of March 2018

- Recruitment across 3 sites (3-4 IBD cases and 3-4 non-IBD controls/centre/month).
- Follow-up of last cases for 3 months (Jan 2019 March 2019)

C. Analyses

- Measurement of faecal VOCs completed by end of March 2019
- Statistical analysis to determine VOCs profiles completed by end of April 2019
- Statistical analysis combining VOCs profile with demographic, clinical and environmental data completed by end of June 2019

D. Writing-up and presentation of findings

• Final report submitted by end of September 2019

STUDY PROTOCOL

Evaluation of faecal volatile organic compounds in the diagnosis of paediatric inflammatory bowel disease

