3.2 Secondary objectives

- To evaluate whether faecal VOCs at initial presentation in children with IBD can distinguish between disease type (Crohn's diseases, ulcerative colitis, indeterminate colitis), distribution and severity
- To evaluate whether faecal VOCs in children with IBD after 3 months of treatment can distinguish those in clinical remission from those with persistent disease
- To explore whether the faecal VOCs identified in paediatric IBD provide new insights into underlying disease mechanisms
- To explore the relationship between fungi, relapse and VOCs.

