3.3 Outcome measures/endpoints

Primary: Faecal VOCs in IBD versus non-IBD gastrointestinal conditions at initial presentation to specialist paediatric gastroenterology review

Secondary:

- Faecal VOCs in children according to IBD diagnosis, distribution and severity at initial presentation
- Faecal VOCs in IBD according to response to treatment at 3 months after diagnosis
- Analysis of likely source of the faecal VOCs that differ between IBD and other GI diseases and correlation with possible disease mechanisms
- Analysis of faecal fungi in relapse of IBD

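### The 3-month treatment-response endpoint is counted from recruitment, from diagnosis and from treatment in different sections, and these dates do not coincide

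*Protocol*

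**What the plan says.** All of the following stands in the current protocol text.

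**Counted from recruitment.** The Trial Summary gives follow-up as "3 months for each child recruited". Section 7.7 says "The clinical records of all children will be reviewed at 3 months after recruitment", and that review records investigation results and diagnoses. Section 7.7 then says "In children with IBD, a further stool sample will be requested at 3 months", without naming a start date. Section 7.8 rules out follow-up beyond 3 months. The schedule in Appendix 4 has a single follow-up visit at 3 months, which carries confirmation of diagnosis, assessment of remission and the second stool sample.

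**Counted from diagnosis.** Section 3.3 lists "Faecal VOCs in IBD according to response to treatment at 3 months after diagnosis". The item heading in section 3.5 and the outcome column of the Trial Summary use the same anchor.

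**Counted from treatment.** The secondary objective in section 3.2 begins "To evaluate whether faecal VOCs in children with IBD after 3 months of treatment can distinguish"; the Trial Summary objective and the text under the heading in 3.5 agree with it. Section 10.7 defines the analysis population as children with IBD "in whom faecal VOCs are analysed 3 months after treatment", read here as after the start of treatment.

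**Timeline.** The study timeline places follow-up of the last cases in January to March 2019 and has "Measurement of faecal VOCs completed by end of March 2019".

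**The concern.** The three starting points are different events. Under section 6.1 a child is recruited when IBD is suspected and further evaluation is still planned. Section 6.2 excludes children already treated for IBD. Section 7.7 bases the diagnosis on endoscopy, biopsy and imaging, and the Background acknowledges that these investigations hold up both diagnosis and treatment. The delay is also likely to vary: section 7.1.1 draws children from out-patient referrals, urgent ward reviews and direct referrals for endoscopy, and section 7.2 sets no limit on the time taken to consider consent.

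If sites follow the operational schedule, the second sample and the activity score will be taken after less treatment than the objective specifies, and after unequal amounts of it. Children classed as having persistent disease could then include more who started treatment late. The endpoint serves one of the three main research questions in section 3. A sample taken at the wrong time cannot be recovered at the analysis stage.

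**Working it through.** **1. Which clock does the timeline fit?** Inputs: recruitment from October 2017 (study timeline), lasting 15 months (section 10.2), with 3 months of follow-up.

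- October 2017 + 15 months = end of December 2018.
- End of December 2018 + 3 months = end of March 2019.

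This reproduces the stated January to March 2019 follow-up of the last cases, so the timeline was built on the recruitment clock. The heading of that timeline block ends recruitment and follow-up in March 2018. That conflicts with the 15 months and with the 2019 follow-up dates, and is not used here.

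**2. Treatment received by a visit timed from recruitment.** Take 3 months as 13 weeks and let d be the weeks from recruitment to the start of IBD treatment. Time on treatment at the visit = 13 − d. The protocol gives no value for d, so the values below are assumptions for illustration.

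| d (weeks) | Weeks on treatment | Share of 13 weeks | Shortfall |
|---|---|---|---|
| 0 | 13 | 100% | 0% |
| 2 | 11 | 85% | 15% |
| 4 | 9 | 69% | 31% |
| 8 | 5 | 38% | 62% |

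The full 3 months is reached only at d = 0. Two children seen at the same nominal visit with d = 2 and d = 8 differ by 11 − 5 = 6 weeks of treatment.

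**3. Calendar effect of counting from treatment.** For a child recruited at the end of December 2018, the second sample falls d weeks after 31 March 2019:

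- d = 2: 14 April 2019
- d = 4: 28 April 2019
- d = 8: 26 May 2019

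Any d above zero passes the stated end-of-March date for completing VOC measurement. On the recruitment clock the objective is missed; on the treatment clock the timetable is missed for the last recruits. Counting from diagnosis gives the same calendar conflict, with d then measured to diagnosis.

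**The case against.** In section 7.7 the words tying the date to recruitment govern only the record review. The stool sample comes in a separate paragraph with no anchor, and section 3.5, which defines the endpoint, speaks of diagnosis and treatment. This stands as a limit: the recruitment anchor for the sample is inferred from the Trial Summary, section 7.8, the single visit in Appendix 4 and the timeline. It does not remove the contradiction, because the endpoint sections also disagree among themselves, and section 3.5 does so within one definition.

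The delays are assumed. Some children are referred directly for endoscopy and may wait little. That also stands, and the table is illustration only.

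A reader might infer that the VOC contrast is biased. The documents do not show this. Remission is judged by activity score at the same visit as the stool sample, so shorter treatment may simply change how many children are in remission. The contrast is biased only if time on treatment affects VOCs apart from disease activity. Confounding is possible; neither its presence nor its direction is established.

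A reader might also infer that late IBD diagnoses are counted as non-IBD and lower the specificity in the primary comparison. Section 10.7 does say "All participants in whom analysis of faecal VOCs is completed will be included in the study analysis", but section 10.3.2 compares confirmed IBD with alternative diagnoses, and nowhere does the protocol say that an unresolved child counts as non-IBD. It gives no time to diagnosis and no rate of unresolved cases, and the handling of such children may be in the separate statistical analysis plan. One can assume, say, 5% hidden IBD and a VOC sensitivity of 0.95, so that a true specificity of 0.80 reads as 0.95 × 0.80 + 0.05 × 0.05 = 0.7625. Both inputs are hypothetical. The sum also treats the test as fixed, whereas section 7.11 derives the model from the study's own labels.

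**Conclusion.** The inconsistency is real. One secondary endpoint has three anchors, and the operational schedule points to the one that does not deliver the time point in the objective. The size depends on a delay the protocol does not state: at assumed delays of 2, 4 and 8 weeks the shortfall is 15%, 31% and 62% of the intended 13 weeks. That treatment duration may confound the remission comparison is a reasonable caution, not a demonstrated bias.

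The primary VOC sample is taken at presentation and is untouched by the contradiction. Diagnoses still unresolved at the 3-month review are a possible but unquantified risk to the primary comparison, and the importance of this point does not rest on them. It should be corrected because it is clear in the text and cheap to repair before samples are collected; it does not threaten the study's main result.

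**What to change.** 1. Reconcile the Trial Summary and sections 3.2, 3.3, 3.5, 7.7 and 10.7, together with Appendix 4, to one anchor for the second research stool sample and activity score. The objective and the analysis population point to the start of IBD treatment.
2. State a window around the 3-month point. Section 7.1.2 promises no extra hospital visits, so the window should be wide enough to use routine attendances.
3. Record the treatment start date. Treatment received is already to be recorded; the case report form is not shown, so this may need only confirmation.
4. Align section 7.8 and the final assay date. With delays of 4 to 8 weeks, the last samples fall in late April to late May 2019, so the VOC profile analysis now due by the end of April 2019 would move as well. The final report is due in September 2019.
5. If samples stay at 3 months after recruitment, restate the endpoint that way and report, or adjust for, time on treatment.
6. For the primary comparison, a sensitivity analysis excluding children without a settled diagnosis at the 3-month review is reasonable.

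The cost is amendment wording, at most one added date on the form, and slightly later assays for the last recruits.
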